**Figure 1 Negative Affect by Genotype and Treatment**

[figure not shown]
abstinence. Smokers carrying the DRD2 A1 allele (A1/A1/A2) quit significantly less often than the homozygous A2s ( $F_{(1,131)}=4.14, p=.04$ ;  $OR=1.82, 95\% CI=1.02, 3.32$ ). This effect was most pronounced during the early weeks of quitting. Moreover, as shown in **Figure 1** we noted a significant pharmacogenetic effect of the drug on negative mood while quitting. Smokers absent the A1 allele (A2/A2) responded to the drug with a substantial reduction in negative affect during the entire post-quitting period for which it was available ( $F_{(1,130)}=6.71, p=.01$ ). These effects were reversed when the drug was withdrawn. In contrast, smokers carrying the A1 allele, showed no significant reduction in negative mood during drug therapy. These results are contrary to what we expected, but if the A1 allele is implicated in reduced DA transmission, the results may be due to the relatively weak DA and NA reuptake properties of venlafaxine. While efficacious in the treatment of depression, in comparison to other antidepressants, venlafaxine is almost 5 times less effective than bupropion at DA reuptake, 10 times less effective at NA reuptake inhibition than nortriptyline and is among the least potent inhibitors of serotonin reuptake of all the SSRIs. We [PCP7]conclude that genotype is important for predicting abstinence but

venlafaxine, and likely other drugs in this class (SSRI) are unlikely to be effective for the control of negative affect during cessation, for the A1 smokers. The current study will ascertain whether bupropion (or nortriptyline) can differentially modify emotional reactivity of A1 or A2 smokers trying to quit, and whether or not this ultimately leads to a better treatment outcome[PCP8].

[figure not shown]
[figure not shown]

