**Modulation of Baseline Startle by Genotype** When we examined baseline startle responding to positive and negative stimuli (adjusted for neutral responses), significant differences ( $F_{(1,58)} = 8.52$ ,  $p=0.0005$ ) were noted by Genotype (A1s vs. A2s). As shown in Figure 4, smokers carrying the A1 allele showed a significantly higher response to both negative and positive stimuli than those with the A2 allele. We also evaluated responding to smoking cues (pictures of cigarettes, people smoking, ash tray, etc.) at baseline and found that overall reactivity to smoking cues was similar in magnitude to that of positive pictures for both groups, although higher responses were observed for the A1s. Interactions with Group (Quit/Control) were not observed. Genotype main effects remained significant when controlling for gender or race. The [pmc13]results suggest that the startle response is a useful tool for detecting baseline (smoking and non deprived) differences in emotional reactivity that at least in part, are genetically mediated. Moreover, taken together with the PANAS data shown in Figure 3, our results suggest that the A1's enhanced emotional reactivity to both negative and positive stimuli seen at baseline, may be assessing a dimension of pre-quitting emotional reactivity not apparent on the baseline PANAS. It may also presage the increased negative affect observed during the first week of quitting for all the A1s but not the A2s in the Quit group.

**Modulation of Startle as a function of Nicotine Withdrawal and Genotype** In this series of

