We estimated power based on 354 subjects and a Type I error rate of 0.05. Power calculations were repeated for each of the three models. For Hypothesis 1, we estimated power for the group contrast between placebo and either bupropion or nortriptyline. A sample size of 354 subjects provides 80% power to detect effect sizes of .17, .32 and .30 standard deviations between these groups for Models 1, 2 and 3, respectively. Given the variability estimates in the raw startle magnitude scores we found by applying the three models to our previous work, these effect sizes translate into group differences in startle magnitude of 4, 22 and 16

µvolts, for Models 1,2 and 3, respectively. These values are well within the range observed in our preliminary studies where the overall difference between treatment and controls averaged 27 µvolts. This range also provides adequate power for detecting interactions with valence for any of the Models, as the range of differences between positive and negative valence between groups, is above 16 µvolts. For Hypothesis 2, we estimated power for the genotype comparisons across a range of possible prevalence for the “at risk” allele, among smokers. The expected allele frequency among smokers is shown in **Table 3**. Data from controls are provided for comparison but except in the case of the NET, are not considered in the power calculations. Power analyses for genotype effects are summarized in **Table 4**. Effect sizes are shown in standard deviation units. The corresponding difference in raw scores (µvolts) is shown in parentheses. Our major hypothesis involving genotype center on the DRD2, for which the A1 is the “at risk allele. As shown in **Table 3**, the expected frequency in our sample of smokers is above 40%. Effect sizes at this frequency and above vary from .15-.30, which corresponds to differences of 3-16 µvolts (see **Table 4**), for the three respective models. In our preliminary studies, the average difference in startle magnitude across all valences between A1 and A2 smokers who quit during the study was 26 µvolts, so we will have adequate power for these comparisons.

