adequate power for detecting 2 way interactions with genotype, for all Models for our primary hypothesis (DRD2), and for our exploratory analysis of other genotypes, if similar results are observed. Our analytic strategy also calls for exploratory analysis of possible interactions between genotype abstinence status (Abstainers Relapsers Never Quitters), and treatment conditions. We expect all smokers in treatment to experience significant startle elevation as a consequence of abstinence or the reduced smoking observed among the Relapsers or Never Quitters, at least through the first week following cessation. If we estimate an overall abstinence rate at the end of treatment of 60%, and an at risk allele frequency of .43 (for the A1), that is the equivalent of a .26 “at risk” allele rate in **Table 5**. Therefore we should be able to detect differences in startle magnitude of 8-43µvolts, depending on the Model, for interactions between genotype, abstinence status and treatment. This range of startle activity also provides us with adequate power to detect interactions with valence, should they occur, as seen in our previous studies. Differences between A1 Relapsers, Never Quitters and Abstainers and A1 Controls across valences ranged from 7 to 40µvolts, across assessments. For A2s the range was more narrow (4-22µvolts). Thus, we should have we should have adequate power to detect interactions with valence, genotype, abstinence and treatment, should they occur.

Power for hypothesis 3 was estimated by dichotomizing emotional reactivity into two groups (high versus low), in order to make use of available standard power formulas. Our actual dependent measure will be a continuous measure of startle, which will offer a much finer gradation of the incremental differences in

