have lower reactivity than A1 placebo users[PCP18]. Homozygous A2s are expected to respond similarly to both drugs with higher levels of emotional reactivity being observed for placebo vs. either bupropion or nortriptyline.

This hypothesis will be evaluated using models similar to those described for hypothesis 1, but with the addition of Genotype (A1/A2 or A1/A1 vs. A2/A2) as a term in each model. We will specifically evaluate the main effect of Genotype first, followed by the Genotype X Group interaction (the term of interest). Other interactions involving Genotype with Days and Valence will be explored as described for Models 2 and 3 above. Planned contrasts involving the difference in startle magnitude between each Group condition, within Genotype, will also be carried out.

3. Higher levels of emotional reactivity of smokers at baseline and or during cessation will be inversely related to abstinence at the 3 and 6 month follow-ups.

- 3.1. Two types of analysis will be carried out. Our primary focus will be on predicting days to relapse. For this analysis, startle responses will serve as the independent variable with days to relapse as the dependent measure. The primary analysis will focus on the average startle response from the baseline assessment. In secondary models, average response to each valence will be included as predictors to determine the relative predictive strength of the different valences. Startle response from each of the post-quit assessments will also be examined as time dependent variables to determine if startle responses from the other assessments predicts relapse. Each model will also be evaluated controlling for or not controlling for treatment Group. For this analysis we will use Cox proportional hazards regression. We are also interested in predicting abstinence (yes/no) at the 3 and 6 month follow-up. Therefore we will also use the GLIMMIX Macro from SAS, which is an adaptation of the PROC Mixed procedure for hypothesis 1 and 2 for dichotomous out come variables (abstinence) to test whether startle responses are related to abstinence, modeling baseline, valence and time dependent characteristics of the model in the manner proposed above. Interactions between genotype (DRD2 A1 vs. A2) and startle in the prediction of abstinence, will also be explored using in the separate and combined valence models.

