Covariates will be included in all models described above to correct for any baseline differences and help improve power. The covariates to be used include ethnicity, age, gender, smoking history, and depression history. Interactions between ethnicity or gender and genotype will be explored. If we find statistically significant interactions, separate models for each ethnicity or gender will also be tested.

The contribution of the WSWS, CES-D, PANAS scores and in-session ratings of craving and mood, to the observed startle effects in the primary hypotheses will be explored by fitting these variables as covariates in the above models. In addition we will examine the relationship between these measures, startle values for each valence, and with in sessions affect ratings using correlational procedures. Changes in these measures over time will also be evaluated using the same Mixed Model approach described above with Group and Genotype serving as between groups factors and Days as the repeated measure. Finally, the primary analyses of the startle magnitude described above will be repeated on the changes in skin conductance response and heart rate to determine the pattern of autonomic arousal displayed for baseline and withdrawal conditions.

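### The Hypothesis 3 models relating startle to relapse omit DRD2 genotype as a main effect, so the startle estimate can partly reflect A1 status; the likely bias is modest and cheap to remove.

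*Combined protocol and SAP*

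**What the plan says.** **A1 and quitting.** Section C (text at Figure 1) reports from a 134-person trial of venlafaxine plus standard care that "Smokers carrying the DRD2 A1 allele (A1/A1/A2) quit significantly less often than the homozygous A2s", with OR 1.82 and 95% CI 1.02 to 3.32. It says the effect was strongest in the early weeks and concludes that genotype matters for predicting abstinence.

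**A1 and startle.** Section C, on modulation of baseline startle by genotype, reports that "smokers carrying the A1 allele showed a significantly higher response to both negative and positive stimuli than those with the A2 allele", after adjustment for the neutral response. The Power section adds that the average difference "across all valences between A1 and A2 smokers who quit during the study was 26" µV.

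**Design.** The Design Summary stratifies the sample on race, gender, history of major depression and DRD2 genotype.

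**Hypothesis 3.** Under Primary Hypotheses, 3.1, the main interest is days to relapse, analysed by Cox regression: "The primary analysis will focus on the average startle response from the baseline assessment". Models are run with and without treatment Group. A GLIMMIX model handles abstinence at 3 and 6 months. Genotype appears once, as an exploratory interaction with startle in predicting abstinence.

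**Covariates.** For all models, "The covariates to be used include ethnicity, age, gender, smoking history, and depression history". Three of the four stratification factors have a counterpart in that list. DRD2 does not.

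**The concern.** Baseline startle is measured, not randomised. Stratifying on DRD2 can balance genotype across the three arms, but it does nothing to separate genotype from startle within the sample. On the sponsor's own data, A1 goes with larger startle and with less quitting. Both links push the unadjusted startle coefficient in the direction that Hypothesis 3 predicts: more reactivity, less abstinence.

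What is at stake is the wording of the conclusion. A significant coefficient would naturally be reported as emotional reactivity predicting relapse. Without a prespecified model containing genotype, the reader cannot tell how much of that is information already available from the DRD2 assay done on every participant. The exploratory interaction does not settle this. It asks whether the startle slope differs by genotype, and it is not stated for the Cox model, which carries the primary analysis.

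**Working it through.** **The plan's own figure.** The Power section states 80% power with 150 per startle group for 48% versus 32% abstinent. Two-sided 0.05, pooled variance under the null:
- SE under null = √(2 × .40 × .60/150) = .0566; SE under alternative = √((.48 × .52 + .32 × .68)/150) = .0558.
- Power = Φ((.16 − 1.96 × .0566)/.0558) = Φ(.88) = 81%. The figure reproduces.

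**Inputs for the bias.**
- N and alpha: "We estimated power based on 354 subjects and a Type I error rate of 0.05" (two-sided assumed).
- A1 carriers: "an at risk allele frequency of .43 (for the A1"; Table 3 gives 42.6%, used here.
- Overall 6-month abstinence 40%, the first scenario in the Power section.
- A1 effect on quitting: OR 1.82, with the confidence limits 1.02 and 3.32 as the range.
- Baseline startle gap: not given in raw units. The Power section gives "effect sizes of .17, .32 and .30 standard deviations between these groups for Models 1, 2 and 3, respectively" and pairs the Model 2 value with 22 µV, so SD = 22/.32 = 69 µV and 26/69 = .38 SD. Assumption: the 26 µV seen among smokers who quit also holds at baseline in everyone.
- Null scenario: startle has no effect within genotype, and the A1 effect on quitting does not run through startle.

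**Step 1, abstinence by genotype.** OR 1.82 with 40% overall gives 31.9% in A1 and 46.0% in A2 (.426 × .319 + .574 × .460 = .40). With exponential relapse times, the A1 hazard ratio is ln(.319)/ln(.460) = 1.47.

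**Step 2, genotype-startle correlation.** √(.426 × .574) = .4945, and .38 × .4945 = .188. Then r = .188/√(1 + .188²) = .185.

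**Step 3, induced Cox coefficient per SD of startle.** Approximately ln(HR for A1) × r × .4945 = .387 × .185 × .4945 = .035, or HR about 1.035.

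**Step 4, rejection rate.** About 60% of 354 relapse, 212 events, so SE is about 1/√212 = .069. The shift is .035/.069 = .51, and Φ(−1.96 + .51) + Φ(−1.96 − .51) = .074 + .007 = 8%.

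**Simulation check** (Cox, N = 354, censoring at 6 months, 4,000 runs, .38 SD gap):

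| A1 odds ratio | HR per SD, unadjusted | Rejection without A1 | Rejection with A1 |
|---|---|---|---|
| 1.00 | 1.00 | 4.7% | 4.4% |
| 1.82 | 1.035 | 7.9% | 5.3% |
| 3.32 | 1.072 | 17.0% | 4.5% |

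At OR 1.02, Step 3 gives about .001, so the rate stays at about 5%. A logistic version at OR 1.82 gave 7.8% without genotype and 4.9% with it, with a spurious OR of about 0.95 per SD.

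**Step 5, size against the powered effect.** With a median split on startle, A1 carriers make up 50.0% of the high group and 35.2% of the low group. The induced abstinence gap is (.500 − .352) × (.460 − .319) = .021, about 2 points. At OR 3.32 (24.3% versus 51.6%) it is .148 × .273 = .040, 4 points. At OR 1.02 it is about 0.1 point. The powered gap is 16 points.

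**The case against.** **Hypothesis 3 is about prediction.** The plan speaks of predicting days to relapse, and the independence it names in the Power section is from treatment, not genotype. As a purely predictive statement, the model without genotype is valid. This stands, and is why the unadjusted model should be kept. But the plan also promotes startle as an endophenotype that reveals more than relapse or genotype alone, and that claim needs the adjusted model.

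**The plan's causal picture is closer to mediation.** If A1 acts on relapse wholly through reactivity, omitting A1 creates no spurious startle effect. This stands too: the 8% assumes the opposite extreme. Adjustment is still safe, because genotype precedes startle and cannot be its consequence.

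**The A1-quitting link is uncertain.** It comes from another trial, its interval starts at 1.02, and the effect was strongest early. The startle pilot found no A1 difference by abstinence status (p = 0.28). That null is weak, however. Only 34 genotyped participants were trying to quit. With 43% A1 and 50% abstinent assumed, OR 1.82 is a difference of about .15 with SE √(.25/14.6 + .25/19.4) = .173, giving power of about 14%.

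**Stronger readings that a reader might infer.**
- That startle would predict relapse only because it tags A1. The documents do not support this. The induced gap is too small, and the text on Figure 5 reports that A1 relapsers exceeded the other A1 groups at baseline, a startle-relapse pattern inside one genotype.
- That genotype is absent from Hypothesis 3. It is not: the exploratory interaction brings it in for abstinence.
- That the startle gap is .47 SD (26/55). That divisor is the Model 3 SD (16/.29 in Table 4), which belongs to post-quit scores controlling for baseline and cannot standardise a baseline score.
- That the gap is about .75 SD, as the pilot F of 8.52 would imply. That F concerns neutral-adjusted responses to negative and positive cues, not the average startle that Hypothesis 3 uses.

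**Conclusion.** The omission is real and its consequence modest. The primary Hypothesis 3 estimate can partly reflect DRD2 genotype, in the predicted direction. At OR 1.82 and a .38 SD gap, the chance of a significant result with no startle effect within genotype is about 8% instead of 5%. It is about 5% at OR 1.02 and about 17% at OR 3.32. Including genotype returns it to about 5%. The induced gap of about 2 points (4 at the upper limit) is far below the 16 points used for power, so genotype is not an alternative explanation for a large startle effect.

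These figures assume that the A1 effect on quitting bypasses startle entirely, that the odds ratio from the venlafaxine trial carries to 6 months, that the 26 µV gap among quitters holds at baseline and can be scaled by the Model 2 SD, that startle is normally distributed, and that relapse times are exponential. To the extent that A1 acts through startle, the bias is smaller. Nothing here makes the unadjusted model wrong as a prediction; it only limits what can be concluded from it.

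**What to change.** In Primary Hypotheses, 3.1:
- Add DRD2 A1 status (A1/A1 or A1/A2 versus A2/A2) as a prespecified main effect in the Cox model for days to relapse and in the GLIMMIX model for abstinence.
- Report the startle coefficient with and without it.
- Base any statement that startle carries information about relapse beyond genotype on the adjusted model, and present the unadjusted model as the purely predictive result.
- Keep the genotype-by-startle interaction exploratory.

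Cost: a sentence or two of text and no new data, since DRD2 is already assayed and used for stratification. The standard error of the startle coefficient rises by 1/√(1 − .185²) = 1.018, about 2%, at a .38 SD gap. A somewhat larger gap would bring it to about 3%.

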**Figure 2 Cigarettes/Day by Abstinence Status**

**Figure 3 Negative Affect Scores by the DRD2 Genotype & Abstinence Status**

**Cigarette Consumption in Relation to Negative Affect**

**During Cessation** Our results showed that daily cigarette consumption did not differ between the Quit (22.5/day) and Control (21.4/day) participants or between A2 (21/day) and A1 (18/day) participants at baseline. However, as shown in **Figure 2**, after the quit date *all smokers* in the Quit group, regardless of Abstinence status (Relapsers, Abstainers and Never Quitters) or Genotype significantly reduced their cigarette consumption ( $F_{(9,92)} = 28.14$ ,  $p = .0001$ - for the Time by Abstinence status interaction). Over the two-week post-quit period, Abstainers dropped to zero cigarettes/day; both Relapsers and Never Quitters averaged well below their baseline; and Controls showed no significant reduction in smoking. At the same time, all smokers in the Quit group, independent of abstinence status, experienced a significant increase in PANAS negative affect scores ( $F_{(9,91)} = 3.99$ ,  $p = .0003$ - for the Time by Abstinence status interaction), reflecting the adverse effects of nicotine withdrawal. Given these facts, some analyses described below include all smokers in the Quit group as well as breakdown by Abstinence status. This practice is often followed in clinical trials that examine the effects of a particular treatment on the post quitting nicotine withdrawal or negative affect for all smokers exposed to the intervention.

**Smoking Negative Affect and Genotype**

A significant group (Quit vs. Controls) by Genotype interaction was observed for PANAS negative affect scores ( $F_{(1,58)} = 10.57$ ,  $p = .0001$ ), with A1 Quit participants being the highest. Baseline differences using an a priori contrast (F-test for simple effects) showed no differences by Group or Genotype. However,

comparisons at subsequent time points showed negative affect of A1s in the Quit group exceeded that of controls while the same was not true of the A2s. Analysis by Abstinence status (Abstainers, Relapsers, Never Quitters and Controls) also showed a significant Abstinence X Genotype interaction ( $F_{(3,54)} = 6.63$ ,  $p = .0007$ ) for

[figure not shown]
PANAS negative affect. Contrasts at each of the sessions revealed that among the A2s, negative affect did not differ by abstinence status, at any time point. However, as shown in Figure 3, among the A1s, Never Quitters and Relapsers experienced the highest level of negative affect followed by Abstainers and then Controls. We repeated this series of analyses controlling for the following variables: hours continuously abstinent at the time each post quit assessment; number of cigarettes smoked in between sessions; race; and gender. No differences in the results were noted.

**Enhancement of Startle to Negative Stimuli at Baseline.** To evaluate the hypothesis that startle responses to negative stimuli would be enhanced compared to neutral and positive stimuli, we first examined the baseline startle responses of all participants. This analysis may be regarded as a validity check for our procedures ensuring that we can replicate the basic valence modulation effect on startle. We used mixed model linear regression with startle amplitude from the baseline session as the dependent variable and valence as the independent variable. The model included the value of the startle response to neutral stimuli as a covariate. In this way, we could compare the relative magnitude of startle responses to negative and positive stimuli, adjusted for the response to neutral cues. A significant effect due to valence was found in the expected direction ( $F_{(1,93)}=44.40$ ,  $p<.0001$ ), with responses to negative stimuli ( $Lsmean=92.66$   $\mu V$ ,  $SE=2.44$ ) being significantly higher than responses to positive stimuli ( $Lsmean=77.23$   $\mu V$ ,  $SE=2.21$ ). No significant differences were noted for main effects due to Group (Quit vs. Controls), gender or race. Thus, all smokers (regardless of group) responded similarly to negative cues at baseline.

**Modulation of Baseline Startle by Genotype** When we examined baseline startle responding to positive and negative stimuli (adjusted for neutral responses), significant differences ( $F_{(1,58)} = 8.52$ ,  $p=0.0005$ ) were noted by Genotype (A1s vs. A2s). As shown in Figure 4, smokers carrying the A1 allele showed a significantly higher response to both negative and positive stimuli than those with the A2 allele. We also evaluated responding to smoking cues (pictures of cigarettes, people smoking, ash tray, etc.) at baseline and found that overall reactivity to smoking cues was similar in magnitude to that of positive pictures for both groups, although higher responses were observed for the A1s. Interactions with Group (Quit/Control) were not observed. Genotype main effects remained significant when controlling for gender or race. The [pmc13]results suggest that the startle response is a useful tool for detecting baseline (smoking and non deprived) differences in emotional reactivity that at least in part, are genetically mediated. Moreover, taken together with the PANAS data shown in Figure 3, our results suggest that the A1's enhanced emotional reactivity to both negative and positive stimuli seen at baseline, may be assessing a dimension of pre-quitting emotional reactivity not apparent on the baseline PANAS. It may also presage the increased negative affect observed during the first week of quitting for all the A1s but not the A2s in the Quit group.

**Modulation of Startle as a function of Nicotine Withdrawal and Genotype** In this series of

